4.2 Randomisation

Randomisation will occur after the participant has provided informed consent and up to four hours after the end of surgery. Participants will be centrally allocated to treatment groups (1:1) by a computer-generated dynamic procedure (minimisation) with a random component. Minimisation variables will be country, surgical procedure category and planned use of epidural anaesthesia. The surgical procedure categories are as follows: (a) resection of colon, rectum or small bowel; (b) resection of liver, pancreas or gall bladder; (c) resection of stomach (non-obesity surgery); (d) resection of oesophagus (non-obesity surgery); (e) obesity surgery; (f) vascular procedure; or (g) other intra-peritoneal surgery. Each participant will be allocated with 80% probability to the group that minimises between group differences in these factors among all participants recruited to the trial to date, and to the alternative group with 20% probability. To enter a patient into the PRISM trial, research staff at the site will log on to a secure web-based randomisation and data entry platform and complete the patient's details to obtain a unique patient identification number and allocation to a treatment group.

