5.4 Secondary outcomes

Secondary outcomes will be analysed using the same approach as the primary outcome (i.e. a mixedeffect logistic regression model, with a random intercept for centre), except they will adjust only for the minimisation variables apart from country (i.e. the model will be adjusted only for planned use of epidural anaesthesia and planned surgical category). This is to avoid over-stratification, as the expected event rate for these outcomes is low. This analysis strategy will be used for the following secondary outcomes:

- 1. Pneumonia within 30 days of randomisation
- 2. Endotracheal re-intubation within 30 days of randomisation
- 3. All-cause mortality within 30 days of randomisation
- 4. Post-operative infection within 30 days of randomisation.
- 5. Postoperative mechanical ventilation (invasive or non-invasive) within 30 days of randomisation.
- 6. All-cause mortality at one year after randomisation

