5.11 Per-protocol analysis

A per-protocol analysis using inverse probability-weighting (IPW) [16] will be performed for the primary outcome and the following secondary outcomes: (a) pneumonia within 30 days of randomisation; (b) endotracheal re-intubation within 30 days of randomisation; (c) all-cause mortality within 30 days of randomisation. Participants who are non-adherent will be excluded from the

analysis; non-adherence is defined as (a) a participant in the intervention group who does not receive any CPAP; or (b) a participant in the usual care group who does receive CPAP. As post-randomisation exclusions can cause bias, we will use weighting to account for baseline risk factors that we expect to be joint determinants of adherence and the outcome. We will use the following baseline covariates to calculate weights: age, current smoker, ASA grade, COPD, interstitial lung disease, bronchiectasis, heart failure, liver cirrhosis, active cancer, previous stroke, respiratory infection within the previous month, planned surgical procedure, planned use of epidural, and BMI. Missing data for these baseline covariates will be handled using mean imputation for continuous variables and the missing indicator approach for categorical variables. The probability of non-adherence will be estimated from on a logistic regression model with non-adherence as the outcome, and the covariates mentioned above as fixed terms. Age and BMI will be included as linear terms. The weight is calculated as $\frac{1}{1-P(non-adherenc)}$; weights will be calculated separately in each treatment group. We will then use the same analysis model as for the main analysis, except we will include the Stata options [pw=weight], and vce(robust).

6. Sensitivity Analysis

We anticipate a very small amount of missing data for the primary outcome. If the level of missing data for the primary outcome exceeds 1% of randomised participants, we will perform a sensitivity analysis to assess the robustness of our analysis of the primary outcome data under the assumption that data is missing-not-at-random (MNAR) [2, 17-19]. For example, this could occur if patients who were discharged home and had no postoperative pneumonia were less likely to respond to their telephone follow-up after 30 days, than patients who did have a postoperative pneumonia.

We will perform a sensitivity analysis assuming the data is MNAR based on the following formula:

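### Country is missing from the per-protocol weights, and from the outcome model for three of the four per-protocol outcomes, so country differences are only partly removed

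*SAP*

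**What the plan says.** SAP 5.11 excludes CPAP-arm patients who received no CPAP and usual-care patients who received any. It gives the purpose of the weights: "we will use weighting to account for baseline risk factors that we expect to be joint determinants of adherence and the outcome". Fourteen baseline covariates are listed, ending with "respiratory infection within the previous month, planned surgical procedure, planned use of epidural, and BMI". Neither country nor centre is among them. On the fitting, "weights will be calculated separately in each treatment group".

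SAP 4.2 names the minimisation factors: "Minimisation variables will be country, surgical procedure category and planned use of epidural anaesthesia". Two of these three are therefore in the weights.

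For the outcome stage, 5.11 says: "We will then use the same analysis model as for the main analysis", with probability weights and robust standard errors added. In SAP 5.3 the primary composite model has country as a fixed factor. In SAP 5.4 the secondary models leave it out: "the model will be adjusted only for planned use of epidural anaesthesia and planned surgical category". The reason given there is over-stratification when outcome events are few. Both models have a random centre intercept, and SAP 5.8 removes that intercept first if a model does not converge.

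**The concern.** Under intention to treat, leaving country out of the secondary models does little harm, because minimisation balances country between the arms. The per-protocol analysis gives up that protection: it removes patients after randomisation, by a different criterion in each arm, so the country mix of those retained can differ between arms.

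Country could plausibly influence both adherence and outcome. Whether CPAP is given depends on local delivery; the SAP's Table 11 collects the delivery method and whether extra research staff helped. Event risk may also differ by country, and the primary model adjusts for country and centre. If countries with poor CPAP delivery also have higher risk, the retained CPAP arm drifts towards low-risk countries and CPAP looks better than it is. If the association is reversed, CPAP looks worse. Removing this kind of imbalance is what the weights are for.

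The reason given in 5.4 does not carry over to the weights. It concerns the number of outcome events, whereas the weight model depends on the number of non-adherent patients.

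**Working it through.** **1. Where country enters**

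| Per-protocol outcome | Country in weights (5.11) | Country in outcome model | Random centre intercept |
|---|---|---|---|
| Primary composite | no | yes (5.3) | yes |
| Pneumonia | no | no (5.4) | yes |
| Re-intubation | no | no (5.4) | yes |
| 30-day mortality | no | no (5.4) | yes |

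**2. Trial size.** The plan's own figure reproduces. With 11.7% against 8.8%, two-sided 5% and 90% power (SAP 4.3), and mean proportion 0.1025:

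n per arm = [1.960·√(2·0.1025·0.8975) + 1.2816·√(0.117·0.883 + 0.088·0.912)]² / 0.029² = 2297.

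Allowing for 4% loss, 2297/0.96 gives 2393 per arm, or 4786 in total, against 4800 stated. Evaluable patients per arm: 2400 × 0.96 = 2304.

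**3. The mechanism by hand.** The SAP gives no country-level figures, so these are assumed (the moderate setting of step 4). True odds ratio 1; usual-care non-adherence 2% in every country.

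| Country | Share | CPAP-arm non-adherence | Risk | Retained = share × (1 − non-adherence) | Events = retained × risk |
|---|---|---|---|---|---|
| 1 | 0.30 | 0.03 | 0.04 | 0.2910 | 0.01164 |
| 2 | 0.15 | 0.08 | 0.06 | 0.1380 | 0.00828 |
| 3 | 0.05 | 0.15 | 0.08 | 0.0425 | 0.00340 |
| 4 | 0.40 | 0.30 | 0.12 | 0.2800 | 0.03360 |
| 5 | 0.05 | 0.20 | 0.10 | 0.0400 | 0.00400 |
| 6 | 0.05 | 0.10 | 0.07 | 0.0450 | 0.00315 |
| Sum | 1.00 | | | 0.8365 | 0.06407 |

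- Retained CPAP-arm risk: 0.06407/0.8365 = 0.0766.
- Usual-care risk (Σ share × risk): 0.0815.
- Crude odds ratio: (0.0766/0.9234)/(0.0815/0.9185) = 0.935, although CPAP has no effect.
- Weighting each retained patient by 1/(1 − country non-adherence) restores the original shares. The CPAP-arm risk returns to 0.0815 and the odds ratio to 1.00.

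**4. What the centre intercept leaves behind.** The per-protocol analysis was simulated with a weighted random-intercept logistic model, true odds ratio 1, 4800 patients, centre SD 0.3 on the logit scale, 400 runs per setting. Weight covariates other than country were taken as unrelated to country. Assumed ranges across countries:

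- Mild: CPAP-arm non-adherence 5–15%, risk 6–10%.
- Moderate: 3–30% and 4–12%.
- Strong: 3–40% and 3–15%, with CPAP use in usual care 0–10%.
- Rare: the same with risks divided by four.

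The last two columns are paired ratios to the analysis with country in the weights and the centre intercept kept.

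| Setting | Centres | Mean OR, as planned | Mean OR, country in weights | Ratio, as planned | Ratio, centre intercept also dropped |
|---|---|---|---|---|---|
| Mild | 40 | 0.994 | 0.998 | 0.995 | 0.989 |
| Mild | 80 | 0.992 | 0.998 | 0.994 | 0.989 |
| Mild, rare | 40 | 1.000 | 1.007 | 0.992 | 0.990 |
| Mild, rare | 80 | 0.991 | 0.999 | 0.991 | 0.989 |
| Moderate | 40 | 0.981 | 0.999 | 0.983 | 0.937 |
| Moderate | 80 | 0.970 | 0.996 | 0.973 | 0.935 |
| Moderate, rare | 40 | 0.965 | 1.000 | 0.965 | 0.939 |
| Moderate, rare | 80 | 0.939 | 0.982 | 0.957 | 0.938 |
| Strong | 40 | 0.972 | 0.997 | 0.975 | 0.849 |
| Strong | 80 | 0.956 | 1.000 | 0.956 | 0.848 |
| Strong, rare | 40 | 0.926 | 0.990 | 0.936 | 0.858 |
| Strong, rare | 80 | 0.903 | 0.985 | 0.916 | 0.860 |

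The share of crude bias that survives the centre intercept is ln(ratio as planned)/ln(ratio with intercept dropped). In the moderate and strong settings it runs from ln 0.975/ln 0.849 = 15% to ln 0.957/ln 0.938 = 69%. Smaller centres and rarer events leave more.

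**5. Against sampling error.** The empirical standard error of the log odds ratio was about 0.11, or 0.22 for rare outcomes. The largest shifts are |ln 0.956|/0.107 = 0.42 and |ln 0.916|/0.227 = 0.39 standard errors. A shift of 0.42 moves a nominal 5% two-sided test to Φ(−1.54) + Φ(−2.38) ≈ 7%.

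**6. A second set of assumptions.** This used 2304 per arm, 60 centres in six equal countries, event rates 2–6%, country SD 0.4–0.7 and centre SD 0.3 on the logit scale. CPAP-arm non-adherence rose with country risk from 2% to 20–35%. Across eight scenarios the planned analysis gave mean odds ratios of 0.97 to 0.99, and adding country to the weights gave 0.99 to 1.02. The paired shift was 1.3% (0.981 to 0.994) to 3.6% (0.966 to 1.002), in the same direction every time. Where non-adherence does not vary by country there is no shift.

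**The case against.** The strongest reply is that the plan already handles most of this. Every per-protocol model keeps a centre intercept and, if each centre lies in one country, it carries country differences too. What remains is shrinkage error in three secondary outcomes of a supplementary analysis. That stands as a limit on importance, but not as an answer: shrinkage is heaviest where events are few, which is the case 5.4 expects for these outcomes.

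The inputs are assumed and rather unfavourable. Non-adherence in 5.11 means no CPAP at all, not short or interrupted CPAP, yet the step 4 settings imply about 10%, 16% and 21% of the CPAP arm receiving none. True rates may be lower or more even across countries. This stands.

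The SAP also never says that country predicts adherence or outcome; its covariate list is a prespecified judgement, and minimisation status alone does not oblige inclusion. That is fair, but the list takes the other two minimisation factors and gives no reason for leaving out the third.

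If local delivery drives non-adherence, centre is the finer unit, and country weights leave differences within a country to the centre intercept. True, but adding country still moves the weights towards their stated aim. In one of the eight step 6 scenarios the mean went from 0.992 to 1.017, further from 1. With a Monte Carlo standard error of 0.007 to 0.015 on the log odds ratio, single means are noisy; the paired shift is the steadier measure.

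Finally, the main analysis in 5.11 could mean the primary-outcome model for all four outcomes, which would restore country. The natural reading is each outcome's own model, but the text should say so.

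**Conclusion.** The point holds. Country is in neither stage of the per-protocol analysis for pneumonia, re-intubation and 30-day mortality, and the centre intercept removes the resulting imbalance only in part. For the primary composite, country stays in the outcome model and the gap is minor. Intention-to-treat results are unaffected.

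The effect is small: under 1% of the odds ratio in mild settings, about 2% to 4% in moderate ones and up to 8% in the strongest, always below half a standard error. Its direction depends on whether countries with poor CPAP delivery have higher or lower risk. These sizes rest on assumed country differences, and the effect is nil if non-adherence does not vary by country. It would matter more if the 5.8 fallback were applied to these models, because nothing would then adjust for country or centre: the ratio to the corrected analysis becomes about 0.94 in the moderate settings and 0.85 to 0.86 in the strong ones. This is a cheap improvement worth making, not a threat to the trial's main conclusion.

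**What to change.** In SAP 5.11, add country as a fixed categorical term to the non-adherence logistic model in each arm. State that patients in any country-arm cell with no non-adherence get weight 1, which is what the weight formula gives when the probability of non-adherence is zero; otherwise perfect prediction could drop them. State also that the main-analysis model means each outcome's own model (5.3 for the composite, 5.4 for the other three). Leave the rest of the weighting and the outcome models as planned.

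The cost is a few phrases in the SAP. Country is a minimisation factor, so it is recorded for every patient. With six countries it adds up to five parameters per arm, and the weights become slightly more variable. Non-adherence may be sparse in the usual-care arm, which is why the empty-cell rule is needed.

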Appendix 1: Deriving outcomes and variables

Variables

At least 'one' co-morbid disease

- Equal to 1if:
 - o At least one of the components of co-morbid disease is marked as 'yes'
- Equal to 0 if all of the components of co-morbid disease are marked as 'no'
- Missing if:
 - o All components are missing
 - OR one or more components of co-morbid disease is missing, and all other components are marked as 'no'

Primary Outcome

Composite endpoint of pneumonia, endotracheal re-intubation or death within 30 days of randomisation.

- Equal to 1 if :
 - The patient experienced an event for one or more of the three components of the primary outcome (pneumonia, endotracheal re-intubation, death), even if data is missing for some of the other components (as in this case, the overall outcome is an event, regardless of the values of the missing components)
 - AND date of event is within 30 days of randomisation (for patients who experience an event for more than one of the three components, the primary outcome will be calculated based on the date of the first event)
- Equal to 0 if:
 - Data is available for each of the three components of the primary outcome
 - AND the patient did not experience an event within 30 days of randomisation
- Missing if:
 - Data is missing for all three components of the primary outcome
 - Data is missing for one or more components, and the patient did not experience an event within 30 days of randomisation for any of the observed components
 - One or more components is marked as 'yes' and is missing the date of the event, and the patient did not experience an event within 30 days of randomisation for the other component(s)

Secondary Outcomes

Pneumonia within 30 days of randomisation

- Equal to 1 if:
 - Pneumonia is marked as 'yes'
 - o AND date of pneumonia is within 30 days of randomisation
- Equal to 0 if:
 - Pneumonia is marked as 'no'
 - OR pneumonia is marked as 'yes' and date of pneumonia is not within 30 days of randomisation
- Missing if:
 - \circ $\;$ Data is not available on whether the patient experienced an event or not
 - o Pneumonia is marked 'yes' and missing date of pneumonia

Death within 30 days of randomisation

- Equal to 1 if:
 - Patient status at 30-day follow-up is dead
 - \circ AND date of death is within 30 days of randomisation
- Equal to 0 if:
 - Patient status at 30-day follow-up is alive
 - OR patient status at 30-day follow-up is marked as 'dead' and date of death is not within 30 days of randomisation
- Missing if:
 - Patient status at 30-day follow-up is missing
 - Patient status at 30-day follow-up is marked as 'dead' and missing date of death

Endotracheal re-intubation within 30 days of randomisation

- Equal to 1 if:
 - Endotracheal re-intubation is marked as 'yes'
 - AND date of endotracheal re-intubation is within 30 days of randomisation
- Equal to 0 if:
 - Endotracheal re-intubation is marked as 'no'
 - OR endotracheal re-intubation is marked as 'yes' and date of endotracheal reintubation is not within 30 days of randomisation
- Missing if:
 - Data is not available on whether the patient experienced an event or not
 - Endotracheal re-intubation marked as 'yes' and missing date of endotracheal reintubation

All-cause mortality at one year after randomisation

- Equal to 1 if:
 - Patient status at one-year follow-up is dead
 - \circ $\;$ AND date of death is within one year of randomisation $\;$
- Equal to 0 if:
 - Patient status at one-year follow-up is alive
 - OR patient status at one-year follow-up is marked as 'yes' and date of death is not within one-year of randomisation
- Missing if:
 - Patient status at one-year follow-up is missing
 - Patient status at one-year follow-up is marked as 'dead' and missing date of death

Postoperative infection within 30 days of randomisation

This is defined as one or more of the following infections (more detail on the definition of each type of infection is available in the PRISM protocol):

- 1) Superficial surgical site infection
- 2) Deep surgical site infection
- 3) Organ space surgical site infection
- 4) Urinary tract infection
- 5) Infection, source uncertain
- 6) Laboratory confirmed blood stream infection
- 7) Pneumonia
- Equal to 1 if:
 - At least one of the components of postoperative infection is listed as occurring (i.e. listed under Clavien-Dindo grade I-V)
- Equal to 0 if:
 - \circ $\;$ All of the components of postoperative infection are "None" $\;$
- Missing if:
 - o All components are missing
 - OR one or more of the components of postoperative infection is missing and all other components are "None"

Postoperative mechanical ventilation (invasive or non-invasive) with 30 days of randomisation

This consists of the following components:

1. Mechanical ventilation (invasive or non-invasive) within four hours of the end of surgery (page

5 of PRISM CRF)

2. Mechanical ventilation (invasive or non-invasive) after leaving the operating room (page 7 of

the PRISM CRF)

- Equal to 1 if:
 - o At least one of the components of mechanical ventilation is "Yes"
- Equal to 0 if:
 - \circ $\;$ All of the components of mechanical ventilation are "No" $\;$
- Missing if:
 - All of the components are missing
 - One or more components of mechanical ventilation is missing, and all other components are "No"

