3.2 Secondary outcome

- Pneumonia within 30 days of randomisation
- Endotracheal re-intubation within 30 days of randomisation
- All-cause mortality within 30 days of randomisation
- Postoperative infection within 30 days of randomisation
- Postoperative mechanical ventilation (invasive or non-invasive) within 30 days of randomisation
- All-cause mortality within one year of randomisation

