5.2.3 Clinical management

Clinical management for the treatment group and usual care group will be summarised but not subjected to statistical testing. Numbers (%) and means (SD) or medians (IQR) will be provided separately for each group. The treatment and usual care groups will be compared for the following clinical management characteristics:

- Surgery: open surgical technique; anaesthetic technique; mechanical ventilation during surgery
- Intravenous fluids during surgery: total intravenous fluid administered excluding blood products; total volume of blood products administered
- Planned and actual level of care on the first night after surgery
- Respiratory support after surgery within four hours of the end of surgery

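### The postoperative ventilation outcome is timed from surgery, so for patients randomised after surgery ended it can count ventilation that preceded randomisation; this dilutes one secondary comparison

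*SAP*

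**What the plan says.** The outcome is listed in SAP section 3.2 as "Postoperative mechanical ventilation (invasive or non-invasive) within 30 days of randomisation". Section 5.4 analyses it with a mixed-effect logistic model, and dummy Table 5 gives it an odds ratio and a p-value.

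Appendix 1 builds it from two case report form items:

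- Component 1: "Mechanical ventilation (invasive or non-invasive) within four hours of the end of surgery"
- Component 2: "Mechanical ventilation (invasive or non-invasive) after leaving the operating room"

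The outcome equals 1 when "At least one of the components of mechanical ventilation is" answered yes. It equals 0 when both are no. No date or time enters the rule.

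On timing of allocation, section 4.2 says: "Randomisation will occur after the participant has provided informed consent and up to four hours after the end of surgery".

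The re-intubation rule in the same appendix adds a condition that the ventilation rule lacks: "AND date of endotracheal re-intubation is within 30 days of randomisation". Pneumonia and death carry the equivalent condition.

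**The concern.** The name of the outcome puts its time origin at randomisation. The derivation puts it at the end of surgery or at leaving the operating room. Where randomisation follows either moment, a stretch of time before allocation falls inside the outcome. A patient briefly ventilated in recovery and then randomised is scored as having the event, although allocation could not have influenced it.

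At stake is the interpretation of one secondary treatment comparison. Events that precede allocation carry no information about CPAP. They raise the event rate in both arms by about the same amount, shrink the relative effect and reduce the chance of detecting it. They can also be unbalanced by chance. The reported result would not be the outcome named in section 3.2.

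**Working it through.** **1. Do the windows overlap?**

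| Item | Clock starts | Stated limit |
|---|---|---|
| Randomisation (4.2) | after consent | up to 4 h after end of surgery |
| Component 1 (App. 1) | end of surgery | 4 h |
| Component 2 (App. 1) | leaving the operating room | none stated |
| Outcome as named (3.2) | randomisation | 30 days |

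For a patient randomised before surgery ended, both components lie wholly after randomisation and there is no fault. For a patient randomised at time *t* after surgery ended, with 0 < *t* ≤ 4 h, component 1 includes the interval from 0 to *t* before randomisation. Component 2 includes any part of that interval spent outside the operating room.

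**2. Does other text close the gap?** The exclusion in section 2.3 covers only anticipated ventilation of at least four hours as part of routine care, so shorter or unplanned ventilation remains possible. Section 1 explains that the word postoperative was added to clarify the period meant. That rules out intra-operative ventilation, but the postoperative period can still begin before randomisation. Section 5.1 analyses all randomised patients with a recorded outcome. Nothing removes the overlap.

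**3. Check of the method on the plan's own figure.** Inputs from section 4.3: 11.7% versus 8.8%, 90% power, two-sided 5%, 4% loss. The two-proportion formula with pooled variance and no continuity correction gives 2297 per arm. 2297 / 0.96 = 2393 per arm, or 4786 in total, against the stated 4800. Evaluable patients per arm are 2400 × 0.96 = 2304.

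**4. Size of the dilution.** The SAP gives neither a ventilation rate nor the share of patients randomised after surgery ended. Assume true post-randomisation rates of 6.0% (usual care) and 4.5% (CPAP), and let *q* be the share of each whole arm ventilated before randomisation. The analysed rates are p₁ = 0.060 + q and p₂ = 0.045 + q. With n = 2304 and p̄ the mean of the two rates:

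OR = [p₂/(1−p₂)] / [p₁/(1−p₁)]

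Power = Φ{ [ (p₁−p₂) − 1.96·√(2p̄(1−p̄)/n) ] / √([p₁(1−p₁)+p₂(1−p₂)]/n) }

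For q = 0: OR = (0.045/0.955)/(0.060/0.940) = 0.74. Power = Φ[(0.015 − 0.01288)/0.00657] = Φ(0.323) = 63%.

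For q = 2%: OR = (0.065/0.935)/(0.080/0.920) = 0.80. Power = Φ[(0.015 − 0.01497)/0.00764] = Φ(0.003) = 50%.

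| q | Analysed rates | OR | Power |
|---|---|---|---|
| 0 | 6.0% v 4.5% | 0.74 | 63% |
| 0.2% | 6.2% v 4.7% | 0.75 | 61% |
| 0.5% | 6.5% v 5.0% | 0.76 | 59% |
| 2% | 8.0% v 6.5% | 0.80 | 50% |
| 3% | 9.0% v 7.5% | 0.82 | 46% |

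As an example of how *q* arises: if 25% of patients are randomised after surgery and 2% of those were ventilated beforehand, q = 0.25 × 0.02 = 0.5%.

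The table treats early and later ventilation as occurring in different patients. If they are independent instead, the rate is q + (1−q)p. At q = 2% the OR stays at 0.80 and power is 49%; at q = 3% they are 0.82 and 44%. The choice changes little.

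**The case against.** The strongest reply is that randomisation protects the comparison. Events before allocation are equally likely in both arms, so the expected error is conservative. That stands. A reader might infer that pre-randomisation events would be credited to CPAP or blamed on it; the SAP does not support that reading.

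The reach is also limited. Section 4.2 sets only an upper limit on the time of randomisation, so an unknown share of patients is randomised early enough to be unaffected. The eligibility criteria reduce the number ventilated early. If *q* is a few tenths of a percent, the loss is two to four points of power. This stands too, and it is why no single magnitude can be claimed.

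A reader might also infer that the 30-day limit is not enforced at all. The documents do not show this. Both components refer to case report form pages that are not reproduced, and the form may set the limit. The postoperative infection rule in Appendix 1 also has no date test, while section 5.7 describes complications as collected within 30 days of randomisation, so a limit can be set at collection. What can be said is that Appendix 1 does not state it for ventilation. For component 1 the upper limit is not at issue.

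Finally, section 5.2.3 lists "Respiratory support after surgery within four hours of the end of surgery" as clinical management without testing. A reader might take this as a contradiction. It is not one: a variable can be both described and used in an outcome, as pneumonia is in dummy Tables 5 and 6.

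None of this removes the mismatch between the outcome's name and its derivation.

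**Conclusion.** The derivation is wrong as written. It can count ventilation that preceded randomisation, through either component, in patients randomised after surgery ended, and it states no 30-day limit. The consequence is dilution towards OR 1 and lost power in one of six secondary outcomes. The primary outcome has its own date rule and is untouched.

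The amount cannot be derived from the SAP. Under the assumed 6.0% versus 4.5% with 2304 per arm, it runs from slight (OR 0.76, 59% power at q = 0.5%) to material (OR 0.80, 50% power at q = 2%), against OR 0.74 and 63% without the fault. These figures rest on the assumed rates, equal *q* in both arms, and an unadjusted two-proportion calculation in place of the planned mixed model.

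**What to change.** In Appendix 1, set the outcome to 1 only if ventilation under either component started after the randomisation time and within 30 days of it. Report ventilation that started earlier descriptively, with the clinical management data. The condition must cover both components: removing component 1 alone would leave the same fault in component 2.

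If start times were not collected, rename the outcome to match what is measured, namely postoperative ventilation from the end of surgery. Add a sensitivity analysis that leaves out the 0–4 hour item for all patients in both arms, and note that component 2 may still contain some pre-randomisation events. Leaving the item out only for patients randomised after surgery is not advisable, because the definition would then depend on when a patient was randomised. Leaving it out at all also loses genuine early events after randomisation, so this belongs in a sensitivity analysis.

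The cost is a change of SAP wording and a date and time check in the derivation code, settled before outcome data are inspected. Fewer events will be counted, by an amount the SAP does not allow one to estimate.
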